11 URGENT SAFETY MEASURES

The Sponsor and Investigator may take appropriate urgent safety measures in order to protect the patients of a clinical trial against any immediate hazard to their health or safety. If such measures are taken by the Investigator they must notify GW immediately or at least within 24 hours of awareness. GW will report urgent safety measures to Competent Authorities by telephone within 24 hours of awareness, wherever possible, and will provide a written report to the Competent Authorities and IRB/EC within 3 days.

12 ADVERSE EVENT REPORTING

12.1 Definitions

12.1.1 Adverse Event

For the purposes of this study an AE is defined as:

Any new unfavorable/unintended signs/symptoms (including abnormal laboratory findings), or diagnosis or worsening of a pre-existing condition, which is present following enrollment (Visit 1) and the post treatment, safety Follow-up visit, which may or may not be considered to be related to the IMP. Any event that is the result of a study procedure must be recorded as an AE.

Surgical/Investigational procedures are not AEs. The medical reason for the procedure is the AE. Elective hospitalizations for pre-study existing conditions or elective procedures are not AEs. The exception may be if the patient has an AE during hospitalization which prolongs their scheduled hospital stay in which case it would be considered a SAE (refer to [Section 12.2](#)).

If reporting a fatal event, the SAE term should be the underlying cause of the death (e.g., disease or medical condition leading to death).

12.1.2 Investigator

The term Investigator refers to the study principal Investigator (PI) or a formally delegated study physician.

12.2 Serious Adverse Events

During clinical investigations, AEs may occur which, if suspected to be IMP-related, might be significant enough to lead to important changes in the way the IMP is developed (e.g., change in dose, population, monitoring need, consent/assent forms). This is particularly true for events that threaten life or function. Such SAEs will be reported promptly to Regulatory/Competent Authorities, applicable IRB/ECs and Investigators (expedited reporting) by GW.

An AE must only be classed as serious, i.e., a SAE, when the event falls into one of the following criteria:

- Results in death.
- Is life-threatening.*
- Requires inpatient hospitalization or prolongation of existing hospitalization.
- Results in persistent or significant disability/incapacity.
- Is a congenital anomaly/birth defect.

- Medically significant.**

* The term “life-threatening” in the definition of “serious” refers to an event in which the patient was at risk of death at the time of the event; it does not refer to an event, which hypothetically might have caused death if it were more severe.

** Medical and scientific judgment should be exercised in deciding whether SAE reporting is appropriate in other situations. Important medical events may not be immediately life-threatening or result in death or hospitalization but may jeopardize the patient or may require intervention to prevent one of the other outcomes listed in the definition above. These should also usually be considered serious. Examples of such events are intensive treatment in an emergency room or at home for allergic bronchospasm; blood dyscrasias or convulsions that do not result in hospitalization; or development of drug dependency or drug abuse.

12.3 Reporting Procedures for Serious Adverse Events

All SAEs occurring during the study must be reported to GW with any other supporting information and recorded in the AE section of the CRF. Any on-going SAEs should be followed up until resolution wherever possible. For all deaths, the working diagnosis or cause of death as stated on a death certificate, available autopsy reports and relevant medical reports should be sent to GW promptly.

All SAEs must be reported directly to GW PVD within 24 hours of discovery or notification of the event. All SAE information must be recorded on the SAE forms provided in the site files and faxed to GW PVD. Additional information received for a case (follow-up or corrections to the original case) need to be detailed on a new SAE form, signed/dated and faxed to the GW PVD and the AE section of the CRF must be updated.

The Investigator should continue to document all AEs which occur up to the last formal follow-up observational period (Follow-up visit). If the Investigator subsequently becomes aware of any new IMP-related SAE after the last formal follow-up period of the study, these should still be reported to the GW PVD.

Any other problem discovered outside these time limits which is deemed to be an unexpected safety issue and is likely to have an impact on patients who have participated in the study, then these should be treated as an SAE and reported to GW PVD. Such post study SAEs do not need to be recorded on the patient’s CRF if editing rights to the CRF have been removed.

Contact details for the GW PVD are provided at the front of the site files for all study centers, and upon the GW SAE Report form.

12.4 Pregnancy

Any patient, or patient's partner, who has become pregnant whilst receiving IMP, or within 90 days of last dose of IMP, must be reported to the GW PVD within 24 hours of first awareness. Please use the GW Pregnancy Monitoring Forms provided. Where possible the Investigator should provide the outcome of the pregnancy.

The Investigator is not obliged to actively monitor for any pregnancies that commence more than 90 days after the final dose of IMP. However, if the Investigator becomes aware of a new pregnancy outside this time limit then they should report it as above. GW PVD will follow up for all pregnancy outcomes.

12.5 Causality Assessment

Causality assessment is required for all AEs and SAEs. Causality assessment must only be assigned by the Investigator. All cases judged as having a reasonable suspected causal relationship to the IMP must be reported as such. The expression "*reasonable causal relationship*" is meant to convey in general that there are facts (evidence) or arguments to suggest a causal relationship.

The following question which must be answered by the Investigator for all AEs is used to capture the reasonable causal relationship of an event to the IMP:

"In your opinion is there a plausible relationship to the IMP?" The answer is "yes", or "no".

Where a pre-treatment event worsens in severity following the first dose of IMP a new event record should be entered into the CRF.

Considering the explanation given above, Investigators are strongly encouraged to express their opinion on what the cause of an AE might be. For individual patients, the Investigator is usually in the best position to assess the underlying suspected cause of an AE. For all AEs and especially SAEs, it is important that the Investigator assess not only the possible role of the IMP but also competing etiological factors as the underlying cause. Factors for consideration may include:

- Medical and disease history.
- Lack of efficacy/worsening of treated condition.
- Concomitant or previous treatment.
- Withdrawal of IMP.
- Protocol-related procedure.

12.6 Reporting Procedures for All Adverse Events

All AEs (including SAEs) occurring during the study will be reported on the running logs in the AE section of the CRF. This includes all events from the time following enrollment (Visit 1) to post study follow-up (Follow-up visit), whether or not attributed to IMP and observed by the Investigator or patient.

For the patient's expected seizure types, these do not routinely require documentation as AEs. However, any worsening, including change in the pattern or severity of seizures must be documented as an AE. Any AE which meets SAE criteria should still be reported as a SAE.

The following information will need to be provided for all AEs:

A) Adverse Event (Diagnosis or Syndrome if Known, or Signs and Symptoms)

Where the Investigator cannot determine a diagnosis, signs or symptoms should be recorded on the AE section of the CRF. Once a diagnosis has been determined the AE section of CRF must be updated to reflect the diagnosis in replacement of the original symptoms. In circumstances, where only a provisional diagnosis is possible (working diagnosis), the CRF must be updated to reflect the provisional diagnosis in replacement of the original symptoms. In some circumstances it may be relevant for the Investigator to include the symptoms alongside the diagnosis in the verbatim event description. However, the diagnosis (full or provisional) should be clearly stated e.g., fever and malaise due to a respiratory tract infection.

B) Adverse Event Start Date and Stop Date

The start and stop dates of the event must be provided. All AEs require these fields to be completed in full. Partial dates or missing dates are not normally acceptable and significant effort must be undertaken to obtain any unknown information. If a precise date is not known an estimated date should be provided instead. When a complete date cannot be given then record as much information as possible (i.e., month and year or in exceptional circumstances just year). When the actual start date becomes known the CRF must be updated to replace the previously recorded date.

C) Outcome

The outcome of the event must be recorded accurately and classified into one of the following categories:

- Recovered.
- Recovered with sequelae.
- Continuing.

- Patient died.

D) Severity

When describing the severity of an AE the terms mild, moderate, or severe should be used. Clinical judgment should be used when determining which severity applies to any AE.

If the severity of an AE fluctuates day-to-day, for example, a headache or constipation, the change in severity should not be recorded each time, instead only the worst observed severity should be recorded with AE start and stop dates relating to the overall event duration regardless of severity.

A severe AE is not the same as a SAE. For example, a patient may have severe vomiting but the event does not result in any of the SAE criteria above. Therefore it should not be classed as serious.

E) Causality

See [Section 12.5](#) above.

F) Action Taken with Study Medication

This question refers to the action taken with the IMP due to an AE. The action with the IMP must be classed as:

- None.
- Dose reduced temporarily.
- Dose reduced.
- Study medication interrupted.
- Study medication stopped.

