9.1.14 Adverse Events

Any adverse changes in the patient’s medical condition, following completion of the consent/assent form by the patient, will be recorded on the CRF as AEs, questioning the patient further if necessary. Any AEs that are continuing from the Core Study will be carried over into the OLE study and transcribed in the CRF, only becoming classified as treatment emergent if they worsen. All AEs occurring during the study, whether or not attributed to the IMP, observed by the Investigator or reported by the patient will be recorded in the CRF.

SAEs must be reported to GW Pharmacovigilance Department (PVD) within 24 hours of discovery or notification of the event, and recorded in the CRF.

Refer to [Section 12](#) for definitions, procedures and further information.

The number of inpatient hospitalizations that are, in the Investigator's opinion, due to epilepsy will be recorded in the patient's CRF and through the SAE reporting process.

Refer to [Section 9.1.15.1.1](#) for the list of 'Triggering AEs of Interest' associated with monitoring of drug abuse liability.

9.1.15 Monitoring of Drug Abuse Liability (for Patients 12 Years of Age and Older)

There are 2 triggers that will require the Investigator or study coordinator to discuss abuse potential signals with the patient or their caregiver. These are either AEs of interest that may be reported by the patient/caregiver, or drug accountability issues regarding overuse of the IMP or missing bottles. Different questionnaires will be completed by the site depending upon which trigger occurs (see [Figure 9-1](#)).

Irrespective of the above, all patients/caregivers will be interviewed at their final dosing visit ('End of Treatment'/Withdrawal visit or 'End of Taper Period' visit, as applicable) and a Study Medication Use and Behavior Survey will be completed by the Investigator or study coordinator. Investigators and study coordinators will be provided with training on how to complete and perform the processes outlined in this section. This training must be completed and documented by the relevant site staff prior to implementation at site.

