13.6.2.1 Adverse Events

AEs will be coded according to the Medical Dictionary for Regulatory Activities dictionary.

A treatment emergent AE is one that started, worsened in severity or seriousness, following the first dose of IMP in this study. Any AEs that are continuing from the Core Study will be carried over into the OLE study and transcribed in the CRF, only becoming classified as treatment emergent if they worsen.

Descriptive presentations of treatment emergent AEs will be given by preferred term and system organ class for the safety analysis set. The number of patients reporting at least one AE will be provided.

The following summaries will be produced:

- Pre-existing AEs.
- All-causality AEs.
- Treatment related AEs.
- All-causality AEs by severity.
- All-causality serious AEs.
- Treatment related serious AEs.
- AEs reported as leading to permanent cessation of study treatment.
- Fatal AEs.

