4.5.2 Adverse Events

All reported AEs will be classified by system organ class (SOC), preferred term and lower level term using Version 17.1 of MedDRA.

Summaries will be presented by SOC and preferred term.

A treatment emergent AE (TEAE) is defined as an AE with a start date on or after the first dose of IMP within this OLE study. If an AE has a partial start date and it is unclear from the partial date (or the stop date) whether the AE started prior to or post first dose of IMP then the AE will be considered treatment emergent. If the start date of the AE is the same as the date of first dose of IMP and the plausible relationship to study medication is marked on the CRF as "Prior to study medication" then the AE will not be considered treatment emergent.

An AE will be considered treatment-related if the plausibility relationship to study medication is recorded on the CRF as 'yes'. If the data on plausibility relationship to study medication is missing then the AE will be considered treatment-related.

An AE will be considered leading to permanent discontinuation of study medication if the action taken with study medication is recorded on the CRF as 'study medication stopped'.

An AE will be considered fatal if the outcome is recorded on the CRF as 'patient died'.

The following summaries will be generated:

- Overall summary of AEs, including number of patients reporting each of; TEAEs, treatment related TEAEs, TEAEs leading to withdrawal, treatment related TEAEs leading to withdrawal, serious TEAEs, treatment related serious TEAEs.
- Summary of TEAEs.
- Summary of treatment-related TEAEs.
- Summary of TEAEs by maximal severity.
- Summary of TEAEs by sex.
- Summary of serious TEAEs.
- Summary of treatment-related serious TEAEs.
- Summary of TEAEs leading to permanent discontinuation of study medication.

- Summary of treatment-related TEAEs leading to permanent discontinuation of study medication.
- Summary of fatal TEAEs.
- Summary of TEAEs by time of first onset of AE.
- Summary of TEAEs by time to AE resolution.
- List of patients experiencing TEAEs by SOC and preferred term.

For the summary of TEAEs by maximal severity, for each patient, the worst severity recorded by preferred term, SOC and overall will be used for summary purposes. If severity is missing, the worst case (severe) will be assumed.

For the summary of TEAEs by time of first onset of AE, data will be summarized under the following categories:

- Weeks 1 to 2 (Day 1 to 14).

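### The AE tables of treatment stops and deaths select events by start date alone, so AEs carried over from the Core Study that end treatment unchanged, or turn fatal on their existing record, are not tabulated

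*Protocol*

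**What the plan says.** **Collection.** Protocol 9.1.14 states: "Any AEs that are continuing from the Core Study will be carried over into the OLE study and transcribed in the CRF". Protocol 12.6 then lists what must be given for all AEs. For outcome, "The outcome of the event must be recorded accurately and classified into one of the following categories": recovered, recovered with sequelae, continuing, or died. For action taken, "This question refers to the action taken with the IMP due to an AE".

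**Protocol definition.** Section 13.6.2.1: "A treatment emergent AE is one that started, worsened in severity or seriousness, following the first dose of IMP in this study". The same section says that a carried-over AE becomes treatment emergent only on worsening. Its planned summaries include pre-existing AEs, AEs that permanently ended treatment, and fatal AEs. Section 12.5 has sites open a new record when a pre-treatment event worsens in severity after the first dose. It has no such rule for seriousness.

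**SAP definition and outputs.** In SAP 4.5.2 a treatment emergent event, TEAE for short, "is defined as an AE with a start date on or after the first dose of IMP within this OLE study"; there is no worsening clause. The outputs include "Summary of TEAEs leading to permanent discontinuation of study medication", the treatment-related version of it, and fatal TEAEs. "An AE will be considered fatal if the outcome is recorded on the CRF as" patient died.

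In SAP Appendix 5, Table 11.1 (overall), Tables 12.3 and 12.4 (stops) and Table 12.5 (deaths) are all TEAE tables. Pre-treatment AEs appear only in Listing 11.2. No table or listing of all deaths is planned. SAP 4.7 itemises departures from the protocol and mentions neither the definition nor the pre-existing AE summary.

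**The concern.** Long-term safety and tolerability is the primary objective, and stops and deaths are among the counts a reader will look at first. Every entrant comes from a placebo-controlled study with at least one active arm, so an AE still running at OLE entry may have begun on GWP42003-P itself. If such an AE ends treatment in the extension, it bears directly on tolerability.

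The SAP rule asks only when the AE began, not when it ended treatment or led to death. An event during OLE treatment can therefore be left out because its record was opened earlier. The study has no data safety monitoring committee (Protocol 14), and interim analyses are to support marketing filings (Protocol 13.2), so the summary tables carry much of the weight.

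**Working it through.** The plan gives no figure to reproduce. The check sets the two definitions against the cases that can arise.

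| AE | TEAE in Protocol 13.6.2.1? | New record under Protocol 12.5? | TEAE in SAP 4.5.2? | In the AE stop or death tables? |
|---|---|---|---|---|
| A. Carried over, worsens in severity, then drug stopped or death | Yes | Yes | Yes, through the new start date | Yes, if coded on the new record |
| B. Carried over, severity grade unchanged, becomes serious or fatal | Yes (seriousness) | No rule | No | No: absent from Table 12.5 if fatal |
| C. Carried over, unchanged, drug stopped because of it | No | No | No | No: absent from Tables 12.3 and 12.4 and the stop count in 11.1 |
| D. Start date partial and unclear | Not addressed | Not addressed | Yes, by SAP rule | Yes |

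**Case B** is a plain mismatch between the documents. An example is a carried-over AE already graded severe, which cannot rise in severity but can become fatal. The same event is also missing from the serious TEAE tables (12.1 and 12.2).

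**Case C** is outside both definitions, so aligning them would not capture it. It needs no worsening: Protocol 12.7 lets a patient withdraw over an AE that the patient finds intolerable.

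**Case A** is less secure than it looks. For AEs whose severity varies from day to day, Protocol 12.6 D asks for one record with the worst grade and dates covering the whole event. The documents do not say whether that rule or the new-record rule governs a carried-over AE.

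**Size per patient.** Planned enrolment is about 680 (Protocol 13.1).

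- Overall column: 1 / 680 = 0.00147, or about 0.15 percentage points for each omitted patient.
- By indication: the planned split is not given. As an assumption, apply the randomised split in SAP Table 1. DS is 34 + 120 + 199 = 353, LGS is 171 + 225 = 396, and the total is 749.
  - DS: 680 × 353 / 749 ≈ 320; 1 / 320 ≈ 0.31 points.
  - LGS: 680 × 396 / 749 ≈ 360; 1 / 360 ≈ 0.28 points.

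**Number of patients.** This would need the share entering with an ongoing AE, and the share of those who stop or die from it on the old record. The documents give neither.

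**The case against.** The best defence is that little is lost.

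- The cut-off includes the day of the first dose, with one exception for AEs marked on the CRF as before study medication, and unclear partial dates count as treatment emergent.
- A rise in severity should generate a new record, so many worsened carried-over AEs are captured.
- All AEs are listed. Listing 11.2 holds pre-treatment AEs, and Listing 12 holds serious AEs and is not restricted to TEAEs by its title. Table 1.2 gives the primary reason for withdrawal in all enrolled patients, so a shortfall against Table 12.3 could be noticed.
- Protocol 13.6.2.1 itself says that the descriptive presentations are of treatment emergent AEs.
- Entrants completed Core Study treatment, and any safety concern at entry is weighed by the investigator, so a stop for an unchanged AE is plausibly uncommon.

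Most of this stands, and it limits the size of the problem. It does not close the gap. Listings preserve cases but give no counts. Table 1.2 gives one reason per patient and no AE terms, and cannot show which AE was involved. The protocol's TEAE framing uses the wider definition and sits beside a planned summary of pre-existing AEs that the SAP reduces to a listing.

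**Conclusion.** The point holds as an incompleteness in the AE tables. A stop for an unworsened carried-over AE, or a carried-over AE that becomes serious or fatal on its old record, is in no AE stop or death table, and SAP 4.7 does not say so. The count cannot be computed. Each patient is worth about 0.15 points overall, or about 0.3 points within an indication under the assumed split. The conclusion assumes that sites follow the recording rules as written.

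A reader might infer more, but the documents do not support it:

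- *Stops are attributed to the wrong AE.* The action field is tied to an action taken because of the AE.
- *Unrelated AEs ongoing at death will be tabulated as fatal.* The outcome has no causal wording, and coding of concurrent AEs at death is not spelled out. But the continuing category is available, and Protocol 12.1.1 makes the fatal term the underlying cause of death. Mis-attribution would need a coding error.
- *A causal death field is already collected.* "Results in death" in Protocol 12.2 is a criterion for classing an AE as serious. The items required for every AE in 12.6 do not include it, so its availability for analysis is not shown.
- *The cases disappear.* They remain in the listings.

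**What to change.** In SAP 4.5.2:

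1. Align the TEAE definition with Protocol 13.6.2.1 by adding worsening in severity or seriousness after the first OLE dose. State how worsening is identified when no new record was opened. This brings in case B.
2. Base Tables 12.3 and 12.4 on every AE whose recorded action is that study medication was stopped during the OLE, with a separate column for AEs that started before the first OLE dose. This brings in case C.
3. Add a summary of all on-study deaths, whatever the AE start date, with one row per patient by underlying cause of death. Protocol 12.1.1 already requires that term for a fatal event, and 12.3 requires cause-of-death information for all deaths.

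If any narrowing is kept, including the reduction of the pre-existing AE summary to a listing, declare it in SAP 4.7.

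The cost is SAP wording, one extra column and one extra table. Action taken, outcome and start date are already required for all AEs. Stop and death counts may become slightly less favourable.
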